2. LIST OF ABBREVIATIONS

AE	Adverse Event
AKI	Acute kidney injury
BP	Blood pressure
CPR	Cardiopulmonary resuscitation
CRF	Case report form
CV	Curriculum vitae
eCRF	Electronic case report form
EDC	Electronic data capture
FDA	Food and Drug Administration
GCP	Good Clinical Practice
ICC	Intraclass correlation
ICF	Informed consent form
ICU	Intensive Care Unit
IRB	Institutional Review Board
ITT	Intention to treat
IV	Intravenous
L/min	Liter per minute
mITT	Modified intent to treat
PLR	Passive leg raise
PPV	Pulse Pressure Variation
RRT	Renal replacement therapy
SAE	Serious adverse event
SV	Stroke volume
SVI	Stroke volume index
SVV	Stroke volume variation
TFC	Thoracic fluid content
TPRI	Total peripheral resistance index
VET	Ventricular ejection time

3. SYNOPSIS

Title:	Evaluation of fluid volume in patients with sepsis and refractory hypotension
Short Title:	FRESH (Fluid Responsiveness Evaluation in Sepsis-associated Hypotension) Fluid Trial
Investigational Device:	Noninvasive Starling™ SV
Objective:	To assess the mean difference in fluid balance and associated patient outcomes, based on a dynamic assessment of fluid responsiveness in septic patients with refractory hypotension in an ICU setting.
Design:	
Multi-center randomized study comparing dynamic assessment of fluid responsiveness utilizing Starling SV compared to a control group.
 
Subjects will be randomized in a 2:1 treatment to control group ratio to increase power for sub-analysis by patient population.
 
Patients randomized to the Starling SV arm will have treatment guided by a dynamic assessment of fluid responsiveness (measured by a change in stroke volume index > +10%) as assessed by passive leg raise (PLR).
 
Patients randomized to the control group will receive standard of care treatment. The use of dynamic fluid assessment (i.e. SVV, PPV, or SV change) to determine fluid responsiveness is prohibited.

Primary Endpoint:	Mean difference in fluid balance (L) at 72 hours or ICU discharge, whichever occurs first, between the two treatment groups
Secondary Endpoints	
 1. Length of ICU stay (days) until subject is medically ready for discharge 2. Number of hours free from ventilator use 3. Requirement for mechanical ventilation 4. Number of hours free from vasopressor use 5. Changes in serum creatinine levels from baseline 6. Requirement for renal replacement therapy (RRT) 7. Mean volume of fluid between the two treatment groups 8. Incidence of Major Adverse Cardiac Event (MACE) 9. Incidence of Adverse Events (AE) 10. Number of ICU readmissions 11. 30 day in-hospital mortality rate 12. Discharge location 13. Mean difference in fluid balance at ICU discharge

Planned Enrollment:	Approximately 210 subjects will be involved in the analysis population
Population:	Patients with sepsis who exhibit refractory hypotension (MAP < 65, or require treatment with vasopressors to maintain a MAP > 65) following initial fluid resuscitation (1L of fluid).
Follow-up Schedule:	Hemodynamic data collection will occur for a 72 hour period starting at the time of study enrollment. Subject outcome data will be collected until the time of hospital discharge.
Number of Sites:	Between 7-15 clinical sites located in the US and 1-3 sites located in the UK
Sub Analysis:	
Primary and secondary endpoints will also be evaluated by the following secondary analysis:
 
 • Patient disease state • Patients determined to be fluid responsive vs non-fluid responsive • AKI measures in patients determined to increase serum creatinine levels from baseline • Enrollment time frame 
Additional sub-analysis will be run as appropriate.

Inclusion Criteria:	
 1. Diagnosis of sepsis, as exhibited by 2 or more of the following SIRS criteria and a known or presumed infection at time of screening: 
 ○ Temperature of > 38 C or < 36 C ○ Heart rate of > 90/min ○ Respiratory rate of > 20/min or PaCO₂ < 32 mm Hg (4.3 kPA) ○ White blood cell count > 12000/mm³ or < 4000/mm³ or >10% immature bands 2. Refractory hypotension (either one single reading of MAP <65 exhibited during the evaluation period, or requiring treatment with vasopressors to maintain a MAP > 65) despite initial fluid resuscitation (1L of treatment fluid) 3. Patient enrolled in study within 24 hours of arrival to the hospital 4. Anticipated ICU admission. Patients may be maintained on another unit (such as within the ER or a step down unit) during the 72 hour monitoring period if the treatment algorithm is adhered to during this time period. 5. Able to provide signed informed consent or consent can be obtained from the patient's authorized representative
Exclusion Criteria:	
 1. Primary diagnosis of: acute cerebral vascular event, acute coronary syndrome, acute pulmonary edema, status asthmaticus, major cardiac arrhythmia, drug overdose, or injury from burn or trauma 2. Known aortic insufficiency, or aortic abnormalities

	
 3. Hemodynamic instability due to active hemorrhage (e.g. gastrointestinal bleeding / coagulopathy / trauma) 4. Patient has received >3 liters of IV fluid prior to study randomization 5. Requires immediate surgery 6. Patient transferred to the ICU from another hospital unit 7. Do not attempt resuscitation (DNAR or DNR) order 8. Advanced directives restricting implementation of the resuscitation protocol 9. Contraindication to blood transfusion 10. Attending clinician deems aggressive resuscitation unsuitable 11. Transferred from another in-hospital setting 12. Not able to commence treatment protocol within 1 hour after randomization 13. Known intraventricular heart defect, such as VSD or ASD 14. Use of additional hemodynamic monitoring involving SVV, PPV, or SV change to determine fluid responsiveness 15. Seizure in the last 24 hours 16. Prisoner 17. Pregnancy 18. Age <18 19. Known allergy to sensor material or gel 20. Inability or contraindication to doing a passive leg raise with both extremities, such as inability to interrupt venous compression boots 21. Patient has an epidural catheter in place 22. Suspected intra-abdominal hypertension 23. Inability to obtain IV access 24. Diabetic ketoacidosis 25. Hyper-osmolarity syndrome 26. Patient treatment uncouples from the treatment algorithm 27. Patient should be excluded based on the opinion of the Clinician/Investigator

Statistical Design:
	
Variables will be tabulated using descriptive statistics. Continuous variables will be presented as number, mean, and standard deviation with 95% confidence intervals, as well as medians and ranges. For categorical variables, relative frequencies and 95% confidence intervals will be provided. Any survival analyses performed will utilize the Kaplan-Meier method.
 
All tests for continuous endpoints utilize a two-sided t-test for difference in two independent means at the overall 0.05 level of significance.
 
The study will be conducted under a common protocol. To evaluate differences among investigational sites in the trial, summary tables by site will be presented and compared.

	Results from the sites will be pooled only if there are no statistical differences between the sites (95% confidence). If variables are found to differ by investigational site, then the variable and/or study site may be identified for special consideration in subsequent analyses.
--	--

**Sponsor/
Manufacturer:** Cheetah Medical, Inc

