7.2 Study Design

This study is a prospective, multi-center, randomized trial comparing the mean difference in fluid balance and associated patient outcomes between a treatment guided by a dynamic assessment of fluid responsiveness and a standard of care control group not using dynamic fluid assessment. Between seven and fifteen sites will be used to enroll 210 subjects with the diagnosis of sepsis and refractory hypotension and in whom the Starling SV system can be attached. Subjects will be randomized in a 2:1 treatment to control group ratio. In the treatment group, a dynamic assessment of fluid responsiveness will be performed at every clinical decision point to treat hypoperfusion or impending hypoperfusion for the first 72 hours of study enrollment. Examples of a clinical decision point include a MAP of < 65, SBP < 90 or blood pressure that is rapidly trending lower, low urine output, or any other clinical indication to administer/alter fluid bolus or pressors. Additionally, an assessment of fluid responsiveness will be performed every 12 hours if no clinical assessments have taken place during this time period.

Fluid responsiveness will be assessed using a passive leg raise (PLR) to guide corresponding treatment (**Appendix A**). Continuous data will be collected from the Starling SV system during the entire treatment period. In the control group, no required therapeutic protocol will be used for patient treatment, and is determined per the discretion of the physician and hospital standards. The use of dynamic fluid assessment (i.e. SVV, PPV, or SV change) to determine fluid responsiveness within the control group is prohibited.

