8. SUBJECT POPULATION AND SELECTION

8.1 Subject Population

[figure not shown]
Adult subjects with the diagnosis of sepsis and refractory hypotension will be considered as a candidate for the study. A maximum of 210 subjects enrolled and in the analysis population will be included in the study. Subjects will be considered to be enrolled when they or their designated representative sign the informed consent form (ICF).

Subjects who are enrolled will be assigned a subject ID. Subjects that sign the ICF, but are found ineligible will be considered screen failures and will be exited from the study at that time. Enrolled subjects who meet study eligibility will be included in the analysis populations and are further described in **Section 12**.

The diagnosis of sepsis is defined as a known or presumed infection and the presence of 2 or more SIRS criteria as detailed in **Section 8.2**. Refractory hypotension is defined as the presence of hypotension following initial resuscitation with 1L of fluid. After obtaining ICF and confirming that the inclusion and exclusion criteria are met, the Cheetah sensors will be placed and connected to the Starling SV monitor. Useable readings will be confirmed prior to initiating the study data collection period.

A diagram outlining the overall subject enrollment plan is shown below:

Figure 1: Subject Flow Diagram

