12. STATISTICAL CONSIDERATIONS

12.1 Sample Size Estimation

Subjects will be randomly assigned in a 2:1 ratio to treatment with Starling SV or to treatment with standard of care. The primary effectiveness endpoint for this study is the difference between the two treatment groups in mean fluid balance at ICU discharge.

Minimum enrollment (N_{\min}) in the study will be set at 120 subjects (80 Starling SV and 40 control) to power at 80% for possible demonstration of superiority for the secondary endpoint of creatinine levels as a measurement of change from baseline. The secondary endpoint for change in creatinine levels at 120 evaluable subjects displays 80% power at a two-sided alpha level of

0.05 to demonstrate superiority under an assumption of a treatment effect of -1.4 mg/dL with a standard deviation of 2.5 mg/dL.

Under an assumption of a treatment effect of -2 L with a standard deviation of 3 L, the sample size of 120 evaluable subjects provides 92.7% power in a test of superiority for the primary effectiveness endpoint.

The trial will incorporate a sample size re-estimation (SSR) at the time of the interim look based on promise for superiority in the key secondary endpoint. Methods for the SSR have been described in detail in previous literature. The maximum enrollment being considered for this trial is 210 total enrolled ($N_{\max} = 1.75 \text{ times } N_{\min}$).

An interim analysis incorporating a SSR will take place when 120 subjects have been enrolled and completed endpoint evaluations. The interim analysis will be performed by an independent statistician. It is assumed that the acute endpoint assessments will be fully informed at the time of the interim analysis.

At this point, the primary study endpoint will be tested as final, and will not incorporate an alpha spend.

The conditional power to claim superiority (CP_{sup}) on the key secondary endpoint for change in creatinine levels will be computed. The conditional power (CP_{sup}) will be calculated based on the interim results of the key secondary endpoint, with the specific interest of demonstrating superiority. CP_{sup} is defined as the approach that quantifies the statistical power to yield an answer different from that seen at the interim analysis. The data will be partitioned into three zones based on CP_{sup} unfavorable zone ($CP_{\text{sup}} < 50\%$), promising zone ($50\% \leq CP_{\text{sup}} < 80\%$), and favorable zone ($CP_{\text{sup}} \geq 80\%$).

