## 3 SEQUENCE OF PLANNED ANALYSES

### 3.1 INTERIM ANALYSES

#### *3.1.1 INTERIM ANALYSES FOR SAMPLE SIZE OF SECONDARY ENDPOINT SUPERIORITY*

The trial will incorporate a sample size re-estimation (SSR) at the time of the interim look based on promise for superiority in the key secondary endpoint of change in serum creatinine from baseline to 72 hours. The maximum enrollment being considered for this trial is 210 total enrolled ( $N_{\max} = 1.75$  times  $N_{\min} = 120$ , where the sample size of 120 is determined as noted in Section 5 below).

The interim analysis on the key secondary endpoint incorporating a SSR will take place when 90 subjects have been enrolled and completed the key secondary endpoint evaluation. The interim analysis will be performed by an independent statistician. It is assumed that the acute endpoint assessments will be fully informed at the time of the interim analysis.

**There will be no inspection of the primary study endpoint at this interim stage. The primary study endpoint will be tested as final at the formal planned final sample size of 120 patients and will not incorporate an alpha spent. In the event of an SSR due to the key secondary endpoint, the primary endpoint will be tested again at the final sample size. No alpha-adjustment is needed across this potential multiple testing of the primary endpoint since the primary endpoint will need to be met at both  $N_{\min}=120$  and, if the sample size is increased to  $>120$ , at the final sample size.**

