After 90 patients have completed the secondary endpoint, the conditional power to claim superiority ( $CP_{\text{sup}}$ ) on the key secondary endpoint for change in creatinine level from baseline to 72 hours will be computed assuming a planned final sample size of 120 patients. The conditional power ( $CP_{\text{sup}}$ ) will be calculated based on the observed interim results of the key secondary endpoint, with the specific interest of demonstrating superiority of the experimental treatment versus the control. The data will be partitioned into three zones based on  $CP_{\text{sup}}$  unfavorable zone ( $CP_{\text{sup}} < 50\%$ ), promising zone ( $50\% \leq CP_{\text{sup}} < 80\%$ ), and favorable zone ( $CP_{\text{sup}} \geq 80\%$ ). If  $CP_{\text{sup}} < 50\%$  or  $CP_{\text{sup}} \geq 80\%$  the study will continue as is. If  $50\% \leq CP_{\text{sup}} < 80\%$  then the sample size may be increased (to a maximum of 210 total) to yield 80%  $CP_{\text{sup}}$  without increasing Type I error, following the methodology of Chen, DeMets and Lan (2004).

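### The protocol synopsis and section 7.2 give 210 as the planned size, although protocol 8.1 and 12.1 and the SAP make 210 only a ceiling and the SAP plans 120

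*Protocol*

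**What the plan says.** Two places in the protocol give 210 as the size of the trial, without condition and without mention of re-estimation:

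- Synopsis, Planned Enrollment: "Approximately 210 subjects will be involved in the analysis population".
- Section 7.2: "Between seven and fifteen sites will be used to enroll 210 subjects with the diagnosis of sepsis and refractory hypotension".

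Two other places in the protocol treat 210 as an upper limit:

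- Section 8.1: "A maximum of 210 subjects enrolled and in the analysis population will be included in the study".
- Section 12.1 sets a minimum of 120 (80 Starling SV, 40 control), attaches both power figures to 120 evaluable subjects, and then says "The maximum enrollment being considered for this trial is 210 total enrolled", defined as 1.75 times the minimum.

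The SAP agrees with the second pair. Section 3.1.1 tests the primary endpoint "at the formal planned final sample size of 120 patients" and computes conditional power on that same final size. If conditional power on creatinine is below 50% or at least 80%, "the study will continue as is". If it lies from 50% to below 80%, the size may be raised, to 210 at most. SAP section 5 repeats 120 as the minimum and 210 as the cap.

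The documents also differ on when the interim takes place. Protocol 12.1 puts it after 120 subjects have completed their endpoints, SAP 3.1.1 after 90. Protocol 12.1 names the three zones but gives no action for any of them.

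**The concern.** The synopsis and the design section are where a site or an IRB looks for planned enrolment. Read alone, they describe a fixed trial of 210. The sample size section and the SAP describe a trial of 120 that may grow to 210 in one interim zone. The gap is 90 subjects, 75% of the smaller figure.

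Normally the protocol's statistical section would resolve such a difference. Here it cannot, because a reader of 12.1 learns that there are three zones but not what final size follows from each.

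Two things are at stake. First, the justification: 210 has no power calculation of its own, and a plan that starts at the cap has no room for re-estimation. Second, the SAP's statement that the increase leaves Type I error intact depends on raising the size only when conditional power is at least 50%. A team that continued to 210 after an unfavourable interim could point to the synopsis and 7.2 for support.

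**Working it through.** **1. Which size the stated powers belong to.** Inputs from protocol 12.1 and SAP 5: 2:1 allocation; two-sided 0.05 (SAP 5); fluid balance effect 2 L, SD 3 L; creatinine effect 1.4 mg/dL, SD 2.5 mg/dL. Two-sample t-test power from the noncentral t, with noncentrality δ / (σ√(1/n₁ + 1/n₂)) and n₁ + n₂ − 2 degrees of freedom.

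| Size | Endpoint | Noncentrality | Power | Stated |
|---|---|---|---|---|
| 120 (80/40) | Fluid balance | 2 / (3 × 0.1936) = 3.443 | 92.7% | 92.7% |
| 120 (80/40) | Creatinine | 1.4 / (2.5 × 0.1936) = 2.892 | 81.8% | 80% |
| 210 (140/70) | Fluid balance | 2 / (3 × 0.1464) = 4.554 | 99.5% | none |
| 210 (140/70) | Creatinine | 1.4 / (2.5 × 0.1464) = 3.826 | 96.8% | none |

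The primary figure reproduces exactly at 120 and the creatinine figure to within 2 points. No stated power belongs to 210.

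**2. Where 210 comes from.** 1.75 × 120 = 210 exactly. It is derived as a cap. If it were also the planned size, the possible increase would be 210 − 210 = 0.

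**3. How often the SAP rule ends at 120.** With the interim at 90 of 120, the information fraction is t = 90/120 = 0.75. I assume conditional power under the observed trend, in line with the SAP's reference to observed interim results: CP = Φ((Z/√t − 1.96)/√(1 − t)). Solving for Z:

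- CP = 50%: Z = √0.75 × 1.96 = 1.697
- CP = 80%: Z = √0.75 × (1.96 + 0.5 × 0.842) = 2.062

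Under the planned creatinine effect, the mean of Z at 90 (60/30) is 1.4 / (2.5√(1/60 + 1/30)) = 2.504. The zone probabilities are then 21.0% unfavourable, 11.9% promising and 67.1% favourable. The SAP's final size is 120 in 21.0 + 67.1 = 88.1% of trials. When the size is raised, it averages about 162.

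**4. Protocol 12.1 taken alone.** With the interim at 120 completed subjects and a final size of 120, t = 1 and √(1 − t) = 0. No data remain, so conditional power is degenerate. The protocol's timing works only with a final size above 120, and 12.1 does not say which.

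**5. Type I error on creatinine.** Simulated null trials, final test at the conventional 1.96, zones defined in the direction favouring Starling SV:

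| Rule | One-sided | Two-sided |
|---|---|---|
| SAP rule: raise to 80% conditional power, cap 210 | 2.4% | 4.9% |
| SAP rule, always to 210 in the promising zone | 2.3% | 4.8% |
| Stop at 120 if favourable, otherwise go to 210 (in neither document) | 3.0% | 5.5% |

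The SAP rule holds its level. The third row is what mixing the two sizes after seeing the interim would cost.

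**6. The unit.** The 210 is total enrolled in protocol 12.1 and SAP 3.1.1, enrolled and in the analysis population in protocol 8.1, and evaluable in SAP 5. Protocol 8.1 counts enrolment from signed consent, so screen failures are enrolled. The primary population in SAP 6.4 is per-protocol, and SAP 9.1 and 9.2.1.1 exclude subjects on dialysis at entry from both powered endpoints. These counts are not interchangeable.

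**The case against.** The strongest reply is that this is not a split between protocol and SAP. Protocol 12.1, the operative section, has 120 as the minimum and 210 as the maximum; 8.1 calls 210 a maximum; the SAP says the same. On that view two summary lines merely lack the words for a ceiling. This is largely right and sets the scope of the point. It does not remove it, because 12.1 gives neither a zone action nor a workable interim timing, and so cannot correct the summary lines.

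Three stronger readings are tempting, and the documents do not support them:

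- *That the instruction to carry on unchanged means 120 or 210 depending on the document.* The instruction occurs only in SAP 3.1.1, in a paragraph that has just fixed the planned final size at 120. There it means 120. The protocol has no such rule.
- *That the promising zone would end smaller than the other two, reversing the rule.* This needs 210 to be the default size outside the promising zone. Protocol 8.1 and 12.1 and SAP 3.1.1 and 5 all call 210 a maximum.
- *That the plan carries a 5.5% error rate.* That figure belongs to a hybrid rule that neither document contains. It would breach the SAP, which also gives the interim to an independent statistician.

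**Conclusion.** The concern holds in limited form. The synopsis and section 7.2 misstate the planned size by 90 subjects against the SAP's 120. Both stated powers rest on 120, and 210 has standing only as the re-estimation cap. Protocol 12.1 leaves the reader without a final size for each zone and sets an interim at which conditional power for 120 cannot be computed.

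The SAP's design is coherent on this point, and following it does not inflate Type I error. The 3.0% one-sided (5.5% two-sided) figure illustrates the cost of a breach and is not a property of the plan. The inconsistency should be corrected, but it does not threaten the validity of the trial if the SAP is followed.

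The power figures rest only on the documents' own effects and SDs. The zone probabilities and error rates also assume observed-trend conditional power, the SAP's interim at 90, and normally distributed test statistics.

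**What to change.** 1. Protocol synopsis and 7.2: replace the flat 210 with *Planned size 120 evaluable subjects; raised, to at most 210 evaluable, only if conditional power on creatinine at the interim is at least 50% and below 80%.*
2. Protocol 12.1: adopt the SAP's interim at 90 evaluated subjects and its action for each zone. This must accompany the first change so that the protocol has one interim timing and one rule.
3. SAP 3.1.1: replace "the study will continue as is" with *the study will continue to the planned 120 evaluable subjects*. It should not say that enrolment stops at 120: the powers need 120 evaluable, and enrolment counted from consent will run higher.
4. Use evaluable as the unit for both 120 and 210 throughout, including protocol 8.1 and SAP 3.1.1.

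The cost is wording in both documents. The planned evaluable number is unchanged from the SAP; the headline size in the synopsis falls from 210 to 120.

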8.3 Exclusion Criteria

Subjects must not have any of the following exclusion criteria:

1. Primary diagnosis of: acute cerebral vascular event, acute coronary syndrome, acute pulmonary edema, status asthmaticus, major cardiac arrhythmia, drug overdose, or injury from burn or trauma
2. Known aortic insufficiency, or aortic abnormalities
3. Hemodynamic instability due to active hemorrhage, (e.g. gastrointestinal bleeding/coagulopathy/trauma)
4. Patient has received > 3 liters of IV fluid prior to study randomization
5. Requires immediate surgery
6. Patient transferred to the ICU from another hospital unit
7. Do not attempt resuscitation (DNAR or DNR) order
8. Advanced directives restricting implementation of the resuscitation protocol
9. Contraindication to blood transfusion
10. Attending clinician deems aggressive resuscitation unsuitable
11. Transferred from another in-hospital setting
12. Not able to commence treatment protocol within 1 hour after randomization
13. Known intraventricular heart defect, such as VSD or ASD
14. Use of additional hemodynamic monitoring involving SVV, PPV or SV changes to determine fluid responsiveness
15. Seizure in the last 24 hours
16. Prisoner
17. Pregnancy

18. Age <18
19. Known allergy to sensor material or gel
20. Inability or contraindication to doing a passive leg raise with both extremities, such as inability to interrupt venous compression boots
21. Patient has an epidural catheter in place
22. Suspected intra-abdominal hypertension
23. Inability to obtain IV access
24. Diabetic ketoacidosis
25. Hyper-osmolarity syndrome
26. Patient treatment uncouples from the treatment algorithm

27. Patient should be excluded based on the opinion of the Clinician/Investigator

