8.6 Subject Randomization

Subjects will be randomized to either the treatment or control arm of the study once the decision has been made to admit the patient to the ICU. Any patients that are enrolled but are not admitted to the ICU, or who receive > 3L of treatment fluid prior to randomization will be considered a screen failure and will be exited from the study at this time.

Subjects will be randomized in a 2:1 treatment to control ratio to increase power for sub-analysis by patient population. Additionally, subject randomization will be stratified to ensure even randomization between the three time windows of enrollment (0-6 hours, 6-12 hours, 12-24 hours)

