## 9.1 PRIMARY EFFICACY VARIABLE

The primary endpoint analysis is an evaluation of the difference between the two treatment groups in mean fluid balance (L) at 72 hours or ICU discharge, whichever occurs first. The following hypothesis will be tested:

$$\begin{aligned}H_0: \mu_c - \mu_t &= 0 \\H_a: \mu_c - \mu_t &\neq 0\end{aligned}$$

where  $\mu_t$  and  $\mu_c$  is the average fluid balance in the Starling SV and control groups, respectively. Statistical summaries will include means, medians, quartiles and standard deviation for each

treatment group, as well as 95% confidence interval of the difference between treatment group means. Subjects that enter the study on dialysis, or are on chronic dialysis, are excluded from this endpoint. A two-sample t-test will be used to test the null hypothesis at a two-sided 0.05 level of significance. A significant p-value combined with a lower sample mean for Starling SV than for the control group will indicate statistical superiority of Starling SV over the control with respect to the primary endpoint. Fluid balance will be analyzed under sensitivity analyses not intended for formal hypotheses testing.

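### Neither document says when the primary fluid balance starts to accumulate; if it starts at enrollment (consent), fluid given before randomisation is counted and the randomised window is shortened.

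*Protocol*

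**What the plan says.** **Endpoint.** SAP 9.1 compares "mean fluid balance (L) at 72 hours or ICU discharge, whichever occurs first". Protocol 7.3.1 and 12.3 and SAP 4.2.1 do the same. All give the end of the window and none gives its start. The test in SAP 9.1 is an unadjusted two-sample t-test.

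**Enrollment.** Protocol 8.1: "Subjects will be considered to be enrolled when they or their designated representative sign the informed consent form (ICF".

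**Windows anchored to enrollment.** The synopsis says "Hemodynamic data collection will occur for a 72 hour period starting at the time of study enrollment". Protocol 7.2 sets guided assessments "for the first 72 hours of study enrollment", and 9.3.2 uses the same anchor. The mITT and per-protocol definitions (protocol 12.2.3 and 12.2.4, SAP 6.3 and 6.4) require treatment-arm monitoring over the first 72 hours of enrollment. Table 1 collects resuscitation fluid at Baseline and again under a column headed Enrollment-72 hours. It has no randomisation column.

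**Randomisation.** Protocol 8.6, where the admission meant is to the ICU: "Subjects will be randomized to either the treatment or control arm of the study once the decision has been made to admit the patient". The same section makes screen failures of "Any patients that are enrolled but are not admitted to the ICU, or who receive > 3L of treatment fluid prior to randomization", so enrolled patients are expected to receive fluid before assignment. Exclusion 4 applies the same ceiling: "Patient has received > 3 liters of IV fluid prior to study randomization".

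**Other anchors.** Protocol 9.3 starts device data collection when usable recordings are obtained. Protocol 10.1 speaks of a 72-hour treatment period. SAP 10.1 counts adverse events from the start of treatment.

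**The concern.** An endpoint that accumulates over time needs a stated time zero. Without one, sites or programmers may count different windows. Enrollment is the most natural reading, because Table 1 collects fluid under that heading and the analysis-set windows use it. On that reading there are three consequences:

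- Fluid given between consent and randomisation enters the endpoint, although arm assignment cannot have influenced it.
- For patients still in the ICU at 72 hours, randomised management lasts less than 72 hours by the length of the gap.
- The monitoring rule that decides membership of the per-protocol set, which SAP 6.4 makes the primary analysis population, opens before any arm exists.

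The stake is precision and dilution in the primary comparison. Pre-randomisation volume, which probably predicts some of the endpoint's variation, is also left unused.

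**Working it through.** **Inputs from the documents.** Effect 2 L, SD 3 L, 80 versus 40 evaluable subjects, two-sided 0.05, stated power 92.7% (protocol 12.1, SAP 5). Qualifying fluid 1 L (inclusion 2). Ceiling before randomisation 3 L (exclusion 4, 8.6).

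**Inputs not in the documents.** The length of the gap, the volume given in it, and the correlation of pre-randomisation volume with the endpoint. The ranges used below are assumptions.

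**Step 1: reproduce the plan's figure.** The standard error is 3 × √(1/80 + 1/40) = 3 × 0.1936 = 0.581 L. The noncentrality is 2 / 0.581 = 3.44. With 118 degrees of freedom and critical value 1.980, the noncentral t gives 92.7%, as stated.

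**Step 2: room for gap fluid.** A patient who consents after the qualifying litre can receive up to 3 − 1 = 2 L more and still be randomised.

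**Step 3: noise.** Let gap fluid have SD s, be independent of later balance, and not already be part of the planned 3 L. The total SD is √(9 + s²).

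| s (L) | Total SD (L) | Power |
|---|---|---|
| 0.5 | 3.04 | 92.0% |
| 0.75 | 3.09 | 91.2% |
| 1.0 | 3.16 | 90.0% |

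The chance imbalance in gap fluid has standard error s × 0.1936, that is 0.10, 0.15 or 0.19 L. It is already contained in these power figures and is not a further loss.

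**Step 4: lost randomised time.** Suppose the 2 L effect refers to a full 72 hours, builds up in proportion to time, and patients stay in the ICU for the whole window. With a gap of g hours the effect is 2 × (1 − g/72), with SD 3 L.

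| Gap (h) | Effect (L) | Power |
|---|---|---|
| 3 | 1.92 | 90.5% |
| 6 | 1.83 | 87.9% |
| 12 | 1.67 | 81.2% |

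A 6-hour gap combined with s = 1.0 L gives 84.4%.

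**Step 5: adjustment.** With correlation r between pre-randomisation volume and the endpoint, the residual SD is 3 × √(1 − r²). For r = 0.3 it is 2.86 L and power is 94.7%. For r = 0.4 it is 2.75 L and power is 96.1%. The degree of freedom spent on the covariate does not change these figures at one decimal.

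**The case against.** The sentence on the 72-hour period governs hemodynamic recordings, not fluid balance, and no passage says that fluid balance runs from consent. Some text points to a later start. Protocol 9.2 places its enrollment procedure after eligibility is confirmed, Table 1 lists Consent, Baseline and Enrollment-72 hours as successive columns, and assessments that apply only to the treatment arm cannot precede assignment. If gap fluid is recorded under Baseline, it may never reach the endpoint. All of this stands. Carry-over is a likely reading and not a stated rule, so the defect is an undefined time zero.

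A reader might infer that gap fluid biases the comparison. It does not: fluid given before assignment is balanced between arms in expectation. Stratification by enrollment window (8.6) may help the balance a little further. A reader might also set the possible 2 L of gap fluid beside the assumed 2 L effect. The first is one patient's maximum and the second is a difference between arm means, so the two are not comparable.

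The time-loss figures lean towards the unfavourable side. Patients who leave the ICU before 72 hours lose no randomised time under either anchor. If the arms diverge mainly in the early hours, the hours lost at the end matter less.

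Finally, an unadjusted t-test is valid in a randomised trial. That is also true; adjustment is recommended for precision and not to repair an invalid test.

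**Conclusion.** The concern holds as a gap in definition with a modest cost. Time zero for the primary endpoint is missing from both documents, and the windows closest to it are anchored to consent, which precedes randomisation by an unlimited interval in which fluid is foreseen. If the enrollment clock is used, the result is noise and dilution, with no systematic difference between arms. Noise alone costs about 1 to 3 percentage points of power for assumed gap-fluid SDs of 0.5 to 1.0 L. Lost time costs about 2 points at an assumed 3 hours and 11 to 12 at 12 hours, if the effect is proportional to time. The documents give neither the volume nor the length of the gap, so these are ranges and not estimates. If the count in practice starts at randomisation, the losses vanish, but the documents still need to say so.

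**What to change.** 1. In protocol 7.3.1 and 12.3 and SAP 9.1, state that the fluid-balance count starts at randomisation.
2. In protocol 12.2 and SAP 6.3 and 6.4, start the 72-hour monitoring requirement for the analysis sets at the same point.
3. Reconcile the 72-hour wording in the synopsis, 7.2, 9.3.2 and Table 1 with these definitions. This concerns the endpoint and the analysis sets; it should leave clinical management unchanged.
4. In SAP 9.1, replace the unadjusted t-test with an ANCOVA that includes total pre-randomisation fluid volume, and bring protocol 12.3 into line. Define the covariate as everything given up to randomisation, because the Baseline entry in Table 1 may stop short of that.

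**Cost.** No added patients or procedures. Sites must already know the pre-randomisation volume to apply exclusion 4 and 8.6, and the randomisation time to apply exclusion 12. Both must be entered explicitly as data. Urine output is recorded every 12 hours (9.3.3), so the plan needs a rule for aligning those records to the randomisation time. The changes should be made before any unblinded look at the primary endpoint.
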